Study Protocol

Study ID : 2019-A02748-49

Title : **Attentional Impairment in People With Epilepsy**

French abbreviation study : ETAPE

Study summary :

Epilepsy is one of the most common chronic neurological conditions. It leads to cognitive impairment in 20-50% of patients with a structural form.

In comparison with seizures, these cognitive disorders are a major additional factor in occupational, social and family disability. They are particularly frequent (50%) in temporal epilepsies and preferably concern memory and language skills.

The cognitive consequences of epilepsy are therefore well described in the following areas: episodic memory, language, executive functions.

Concerning attentional abilities, a recent review has highlighted the lack of work in this specific field in order to properly measure the prevalence and nature of attentional disorders in epileptic patients. Indeed, attentional abilities are often mentioned in studies, but attention is a complex domain defined by four modalities: alertness, selective attention, divided attention and sustained attention. No study systematically assesses all of these modalities.

The objective of this study is to evaluate the prevalence and nature of attentional disorders in epileptic patients compared to control subjects.

- **Primary outcome** : To evaluate the prevalence of attentional disorders in epileptic patients compared to control subjects.
- **Secondary outcome** : Assess the nature of attentional disorders in relation to executive functions and the level of anxiety-depression.
- **Main endpoint** : D2 task (selective attentional task)
- **Other measures** : attentionnal task (see below); executive task and depression and anxiety scale (total duration : around one hour and 10 minutes)

Attentional tasks description :

Selective attention
 
D2
 
Test duration: 5 minutes
	

Subtests
 
Alertness
 
TAP 2.2 – Alertness
 
Test duration: 5 minutes
	
Examples
 
Alertness
 
Please note: The test will be conducted in two ways:
 
First condition: A cross appears on the screen. Please press the key when the cross appears!
 
Second condition: You will hear a signal and then the cross will appear. Please press the key only when the cross appears !
 
Please press a key (cancel with X)


Divided attention
 
TAP 2.2 – Divided attention
 
Test duration: 6 minutes
	
Divided Attention / dual task
 
You have two tasks in this test:
 
First task: You will see a region on the screen in which a varying number of crosses appear simultaneously. When four of these crosses form a square, then please press the key as quickly as possible.
 
Example:
 <pre> x . x . x . x x . . x x . x . . </pre> 
Second task: In this task you will hear a high and a low tone in sequence. You must decide whether the same tone occurs twice in a row. Please press the key as quickly as possible!
 
Your task is to pay attention to both squares and tones at the same time.
 
Please press a key (cancel with X)

Sustained attention
 
TAP 2.2 – Sustained attention
 
Test duration: 15 minutes
	
Sustained Attention
 
In the following test, you will see patterns of different shapes, colours and sizes on the screen:
  
Your task is to press the key as quickly as possible whenever two successive patterns have the same shape.
 
Please press a key (cancel with X)

Executives task :

Digit span

Verbal fluencies

Inhibition task : subtest incompatibility in TAP battery

Flexibility task : subtest flexibility in TAP battery

Scales :

Neurological Disorders Depression Inventory for Epilepsy (NDDI-E)

Generalized Anxiety Disorder (GAD-7)

Population : Epileptic patients versus normal control

The inclusion criteria for patients are:

- Patients with epilepsy, according to the Fisher et al. (2005) criteria.
- Patient with written informed consent
- Affiliation to a social security insurance
- Individuals who have received full information about the organization of the research and have not objected to their participation and the use of their data.
- Person 18 years of age and older

The inclusion criteria for healthy subjects are:

- Individuals who have received full information about the organization of the research and have not objected to their participation and use of their data.
- Person 18 years of age and older
- Person with no neurological and/or psychiatric history

Duration of the inclusion period: 5 years

Duration of subject participation (2 visits): There may be a delay of up to 3 months between the inclusion visit with neurological screening and the planning of the neuropsychological assessment visit after which the subject exits the study.

Total research duration: 5 years and 3 months.

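### The primary objective covers attentional disorders in general, but the only main endpoint (D2) measures selective attention, one of the four modalities the protocol names

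*Protocol*

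**What the plan says.** All the governing text is in the Protocol's Study summary.

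- The rationale states that "attention is a complex domain defined by four modalities: alertness, selective attention, divided attention and sustained attention", and gives as the gap in earlier work: "No study systematically assesses all of these modalities".
- The primary objective, listed under Primary outcome, is "To evaluate the prevalence of attentional disorders in epileptic patients compared to control subjects". It is not restricted to any modality.
- The Main endpoint line names one test: "D2 task (selective attentional task". The attentional task table again files D2 under selective attention.
- The remaining attention tests come under Other measures: "attentionnal task (see below); executive task and depression and anxiety scale". The task table shows that these are the TAP 2.2 subtests for alertness, divided attention and sustained attention.
- The secondary objective concerns the nature of the disorders as they relate to executive function and mood. It does not ask for the prevalence of impairment in the other three modalities.

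**The concern.** The protocol argues that attention is not a single ability and that earlier work fell short by not assessing all of its parts. It then rests its primary question, about the whole domain, on a test that it assigns to one part.

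At stake is what the primary result can support. A D2 difference between groups is evidence about selective attention and would not give the overall prevalence of attentional disorders. A D2 comparison showing no difference would leave three of the four modalities unaddressed, so it could not be read as no excess of attentional disorders even if it were very precise. Someone who takes the primary objective at its word could draw either conclusion.

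**Working it through.** **1. Text comparison.** The mismatch itself needs no arithmetic.

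| Element | Scope in the Protocol |
|---|---|
| Definition of attention | Four modalities |
| Primary objective | Attentional disorders, unrestricted |
| Main endpoint | D2: selective attention only |
| Alertness, divided, sustained attention | Tested; listed under Other measures |

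Three things could reconcile the second and third rows: a sentence limiting the objective to selective attention, a statement that D2 represents attention overall, or a rule combining the four tests. The document contains none of them. A separate analysis plan could supply a D2 score and cut-off, but the result would still be selective-attention impairment.

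**2. Plan's own figure.** There is none to reproduce. The Protocol gives no impairment rate, cut-off, correlation, sample size or rule for calling a person impaired.

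**3. Illustration; every rate is assumed.** Controls: 5% impaired on each test. Patients: 20% on each affected test, 5% on each unaffected one. The four tests share an equal latent correlation ρ of 0, 0.3, 0.5, 0.7 or 0.9. Two possible rules for an attentional disorder are tried: impaired on at least one of four tests, and on at least two.

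Given a common standard normal factor f, test j with marginal rate pⱼ is impaired with probability

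qⱼ(f) = Φ( (Φ⁻¹(pⱼ) − √ρ·f) / √(1−ρ) ).

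Then P(at least one) = 1 − ∫ ∏(1 − qⱼ(f)) φ(f) df. P(at least two) subtracts the probability of exactly one as well.

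At ρ = 0 this can be done by hand.

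At least one of four:
- Controls: 1 − 0.95⁴ = 0.186
- D2 spared, other three affected: 1 − 0.95 × 0.80³ = 0.514
- Only D2 affected: 1 − 0.80 × 0.95³ = 0.314
- All four affected: 1 − 0.80⁴ = 0.590

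At least two of four:
- Controls: 0.186 − 4 × 0.05 × 0.95³ = 0.014
- D2 spared: 0.514 − (0.05 × 0.80³ + 3 × 0.20 × 0.95 × 0.80²) = 0.514 − 0.390 = 0.123 (from unrounded terms)
- Only D2 affected: 0.314 − (0.20 × 0.95³ + 3 × 0.80 × 0.05 × 0.95²) = 0.314 − 0.280 = 0.034
- All four affected: 0.590 − 4 × 0.20 × 0.80³ = 0.181

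Over ρ = 0 to 0.9, by numerical integration:

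| Pattern in patients | D2, patients vs controls | At least one, patients vs controls | At least two, patients vs controls |
|---|---|---|---|
| D2 spared, other three affected | 5% vs 5% | 28–51% vs 9–19% | 12–19% vs 1–5% |
| Only D2 affected | 20% vs 5% | 20–31% vs 9–19% | 3–8% vs 1–5% |
| All four affected equally | 20% vs 5% | 30–59% vs 9–19% | 18–23% vs 1–5% |

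Differences between groups at the same ρ, in percentage points:

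| Pattern in patients | D2 | At least one | At least two |
|---|---|---|---|
| D2 spared, other three affected | 0 | 19–33 | 11–14 |
| Only D2 affected | 15 | 11–13 | 2–3 |
| All four affected equally | 15 | 21–40 | 17–18 |

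Depending on the pattern and the rule, D2 misses the broader difference, exceeds it, or comes close to it.

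**The case against.** Serving a broad objective with one main test and several supporting ones is a common and legitimate structure. It avoids an arbitrary combination rule, which has its own price: under at-least-one-of-four, the assumed 5% in controls becomes 9–19%. The restriction is also visible, since the endpoint line itself labels D2 as selective. The rationale asks that all four modalities be assessed, and this study does assess them; it does not say that all four must be primary. The two one-sided patterns above are extremes. If all four modalities are equally affected, D2 differs by 15 points against 17–18 for at least two of four, which is close agreement. On this view a single qualifying word would settle the matter.

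Much of this stands. D2 is an acceptable endpoint, the label lowers the risk of misreading, and the remedy is a matter of wording. The equal-impairment case shows that D2 need not mislead, although even there it understates the at-least-one difference (21–40 points). None of this closes the gap. One test can represent a broad construct if the plan says so and justifies it, whereas this plan argues that the construct has four parts. Which impairment pattern holds is what the study sets out to learn, so agreement between D2 and the wider domain cannot be presumed.

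**Conclusion.** The concern holds and should be fixed. As worded, the primary objective claims more than its endpoint measures, and an analysis plan that sets only how D2 is scored would not change that. This conclusion rests on the Protocol's text alone.

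The size is an illustration under assumed rates (5% and 20% per test, ρ from 0 to 0.9). D2 could show no difference where the at-least-one rule shows 19–33 points, or show 15 points where the broader rules show 11–13 or 2–3. The harm is limited because the other three modalities are measured and D2 is labelled openly. The fault lies in the pairing of objective with endpoint, not in data collection.

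**What to change.** Reword the primary objective, and the claim to be drawn from it, as the prevalence of selective-attention impairment on D2 in patients compared with controls. Report alertness, divided attention and sustained attention beside it as secondary results.

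The rewording needs no new data and no change of endpoint. Its cost is a headline narrower than the four-modality rationale. Reporting the TAP tests as impairment prevalences takes some work, because each needs one score and cut-off chosen in advance. For alertness, "The test will be conducted in two ways", and for divided attention, "You have two tasks in this test", so in both a choice between components has to be fixed.

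If the sponsor prefers to keep the broad objective, the alternative is one primary endpoint over all four tests, with the rule for calling a person impaired defined before any data are examined. That needs the same score and cut-off choices plus a combination rule. It also changes the expected rates in both groups, and with them any sample-size basis (none is shown in the Protocol). It is an option for the sponsor to weigh, not the required correction.

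### Does relying on an epilepsy-specific depression inventory leave the secondary objective without a usable depression measure in a patient-control study?

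*Protocol*

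**What the plan says.** The Scales list of the protocol has two entries: the "Neurological Disorders Depression Inventory for Epilepsy (NDDI-E") and the "Generalized Anxiety Disorder (GAD-7"). The first is the only depression measure in the document; the second concerns anxiety.

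The Study summary sets the general aim: "The objective of this study is to evaluate the prevalence and nature of attentional disorders in epileptic patients compared to control subjects". Beneath it, the primary outcome is the prevalence of attentional disorders in patients against controls, with the D2 task as main endpoint. The secondary outcome reads: "Assess the nature of attentional disorders in relation to executive functions and the level of anxiety-depression". The scales appear under Other measures as part of one battery: "executive task and depression and anxiety scale (total duration : around one hour and 10 minutes").

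The design line is "Population : Epileptic patients versus normal control", and healthy subjects must meet the criterion "Person with no neurological and/or psychiatric history". The protocol does not say whether the scales go to patients only or to both groups, and it describes no statistical model.

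**The concern.** Four facts together look like a mismatch. The study has two groups. A single battery is listed without assigning any part of it to one group. The only depression scale is, by its name, meant for one group. The general aim places the nature of attentional disorders, as well as their prevalence, in the comparison with controls.

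The eligibility criteria add to the worry. Controls are screened for psychiatric history, while the listed patient criteria contain no such condition. The groups may therefore differ in depression through selection, and depression becomes a rival explanation for poorer attention in patients. If NDDI-E scores meant different things in the two groups, adjusting for them or pooling on them could leave confounding in place or add measurement error that depends on group. The study could then not say whether an attentional deficit is explained by depression.

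**Working it through.** No arithmetic applies. The protocol gives no sample size, effect size or model, and nothing about the scale's performance. The check is a reading of the relevant places against each other.

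1. **What the secondary outcome asks for.** The primary outcome names the control group as comparator. The secondary outcome, the next line of the same list, does not. It asks how the nature of attentional disorders relates to executive function and mood: "Assess the nature of attentional disorders in relation to executive functions and the level of anxiety-depression". That is an association, most naturally examined among people who may have such disorders, chiefly the patients. It does not promise to adjust the patient-control difference for depression.

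2. **Whether the general aim forces a cross-group depression analysis.** The general aim does compare nature with controls. The Study summary, however, describes attention through four modalities: alertness, selective, divided and sustained attention. Showing which of these are affected in patients relative to controls requires the attention tests. It does not require a depression score in controls. Relating the pattern to mood is the further step named in the secondary outcome, and that step has no stated comparator.

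3. **Whether a vulnerable analysis is planned.** The harm needs NDDI-E to be used as a covariate in the group contrast, as a pooled predictor or as a between-group outcome. None of these appears in the protocol. Listing one battery does not imply any of them: a scale can be given to everyone and analysed in one group.

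4. **Whether the scores are shown to be non-comparable.** The only evidence in the document is the name. A name tells the reader the intended population. It does not show that the items measure something different in other people. With no items, cut-offs or data outside epilepsy, neither comparability nor its absence can be established here. The same limit applies to the assumption that the GAD-7 works equally in both groups.

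5. **Whether the possible changes meet the stated harm.** Restricting NDDI-E analyses to patients and using the GAD-7 for the two-group question would still leave depression out of the patient-control contrast. It would only record an analysis population, which a statistical analysis plan commonly does. Adding a general depression questionnaire for both groups would address the contrast, but it widens the study's question beyond what the secondary outcome states. That is a design preference, not the correction of an error.

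6. **Reach.** The primary outcome and the D2 endpoint do not use the NDDI-E. The most that could be affected is one of two mood factors in one secondary outcome.

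**The case for a change.** The strongest argument on the other side is about data collection. The choice of questionnaire is fixed before testing, and each subject leaves the study after the neuropsychological visit. A later analysis plan can restrict how NDDI-E scores are used, but it cannot recover a general depression score that was never collected. With psychiatric history screened only in controls, the wish to examine depression as a rival explanation is reasonable.

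Part of this stands. The protocol does not say that the depression analysis is confined to patients, the general aim does mention nature alongside controls, and an uncollected measure cannot be added afterwards. If the investigators intended to explain the group difference by depression, they would need to be satisfied that their scale serves both groups.

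It does not make the present choice wrong. The argument supplies an aim, explaining the group contrast by depression, that the protocol does not state, and then faults the instrument for not serving it. The difference in screening is a feature of control selection, and it would remain whichever depression scale was used. Excluding psychiatric history probably also narrows the range of depression scores among controls on any scale, although it does not rule out current symptoms.

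**Conclusion.** The concern does not hold. The facts behind it are correct: the NDDI-E is the only depression scale, it is named for epilepsy, and the study includes healthy controls. They do not amount to an error or a contradiction, because the protocol states no cross-group use of the score and its secondary outcome is met by an association within patients, which is where the scale fits.

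No magnitude can be derived from the document. The conclusion rests on two assumptions: that the secondary outcome is read as worded, without a comparator, and that the choice of group for the mood analysis belongs to a statistical analysis plan that is not available here. If that plan were to pool NDDI-E scores or adjust the patient-control contrast for them, their comparability across groups would have to be justified there. That would be a question about that plan, and the present document cannot settle it.
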